### ***Pneumonitis***

Out of a total of 1562 subjects, pneumonitis was identified in 45 subjects (2.9%), of which 42 (2.7%) were considered drug related. Serious events were identified in 1.2% of subjects, and all serious events were considered by the Investigators to be drug related. One subject died due to pneumonitis (interstitial lung disease). Fourteen subjects (0.9%) experienced Grade 1 pneumonitis, 15 subjects (1.0%) experienced Grade 2 pneumonitis, 11 subjects (0.7%) experienced Grade 3 pneumonitis, and 2 subjects (0.1%) experienced Grade 4 pneumonitis. For “interstitial lung disease,” 1 subject (0.1%) experienced Grade 1 interstitial lung disease, 1 subject (0.1%) experienced Grade 3 interstitial lung disease, and 1 subject (0.1%) experienced Grade 5 interstitial lung disease. A high initial dose of corticosteroids was used in 21 subjects, while a low initial dose of corticosteroids was used in 5 subjects.

### ***Vasculitis***

Out of a total of 1562 subjects, vasculitis was identified in 2 subjects (0.1%); both cases were considered drug related. The events were identified as serious for one subject (0.1%). The two instances of vasculitis were Grade 1 and Grade 3.

### ***Common adverse events***

The most commonly reported treatment-emergent AEs in pembrolizumab monotherapy trials are fatigue (35.4%), nausea (13.8%), decreased appetite (13.8%), diarrhea (12.3%), constipation (10.8%), and AST increase (10.8%). In combination therapy trials, the most commonly reported treatment-emergent AEs across the dose regimens were neutropenia and thrombocytopenia (50.0% each), anemia (30.0%), dysphonia, hiccups, and pruritis (20.0% each). Most of these events also have been mild to moderate in severity. The incidence of grade 3-5 treatment-emergent AEs ranges from 6.8-12.0% in monotherapy trials, and 23.1-50.0% in combination therapy trials. The above is preliminary safety information. The information has been reviewed, but has not been completely monitored; therefore, changes may occur to the safety information may occur going forward. Safety information will continue to be collected and evaluated as the study continues.

### ***Potential for Drug-Drug Interactions***

No formal pharmacokinetic drug interaction studies have been conducted with pembrolizumab.

### ***Contraindications***

None.

#### **11.2.2. Risks related to decitabine**

In a single-arm MDS study (N=99) decitabine was dosed at 20 mg/m^2 intravenous, infused over one hour daily for 5 consecutive days of a four week cycle. Listed below are all adverse events reported, regardless of causality, occurring in at least 5% of patients.

**Blood and lymphatic system disorders**

- Anemia
- Febrile neutropenia
- Leukopenia
- Neutropenia
- Pancytopenia
- Thrombocythemia
- Thrombocytopenia

**Cardiac disorders**

- Cardiac failure congestive
- Tachycardia

**Ear and labyrinth disorders**

- Ear pain

**Gastrointestinal disorders**

- Abdominal pain
- Abdominal pain upper
- Constipation
- Diarrhea
- Dyspepsia
- Dysphagia
- Gastro-esophageal reflux disease
- Nausea
- Oral pain
- Stomatitis
- Toothache
- Vomiting

**General disorders and administration site conditions**

- Asthenia
- Chest pain
- Chills
- Fatigue
- Mucosal inflammation
- Edema
- Edema peripheral
- Pain
- Pyrexia

**Infections and infestations**

- Cellulitis
- Oral candidiasis
- Pneumonia
- Sinusitis
- Staphylococcal bacteremia
- Tooth abscess

- Upper respiratory tract infection
- Urinary tract infection

**Injury, poisoning and procedural complications**

- Contusion

**Investigations**

- Blood bilirubin increased
- Breath sounds abnormal
- Weight decreased

**Metabolism and nutrition disorders**

- Anorexia
- Decreased appetite
- Dehydration
- Hyperglycemia
- Hypokalemia
- Hypomagnesemia

**Musculoskeletal and connective tissue disorders**

- Arthralgia
- Back pain
- Bone pain
- Muscle spasms
- Muscular weakness
- Musculoskeletal pain
- Myalgia
- Pain in extremity

**Nervous system disorders**

- Dizziness
- Headache
- Psychiatric disorders
- Anxiety
- Confusional state
- Depression
- Insomnia

**Respiratory, thoracic and mediastinal disorders**

- Cough
- Dyspnea
- Epistaxis
- Pharyngolaryngeal pain
- Pleural effusion
- Sinus congestion

**Skin and subcutaneous tissue disorders**

- Dry skin
- Ecchymosis
- Erythema

- Night sweats
- Petechiae
- Pruritus
- Rash

- Skin lesion

#### **Vascular disorders**

- Hypertension
- Hypotension

### ***Potential for Drug-Drug Interactions***

Drug interaction studies with decitabine have not been conducted. In vitro studies in human liver microsomes suggest that decitabine is unlikely to inhibit or induce cytochrome P450 enzymes. In vitro metabolism studies have suggested that decitabine is not a substrate for human liver cytochrome P450 enzymes. As plasma protein binding of decitabine is negligible (<1%), interactions due to displacement of more highly protein bound drugs from plasma proteins are not expected.

### ***Contraindications***

None.

#### **11.2.3. Risks related to blood draws**

No major risks are involved with blood draws. Minor complications including bleeding, pain, and hematoma formation at the site of blood draws, vasovagal reactions or infections may rarely occur.

#### **11.2.4. Risks related to CT scans**

CT (computed tomography) scanning is performed as part of the clinical standard of care and does not have a research use in this protocol. CT uses special x-ray equipment to obtain image data from different angles around the body and then uses computer processing of the information to show a cross-section of body tissues and organs. Oral and/or intravenous contrast agents will not routinely be used on this study. Contrast agents may be used medically indicated to due unique clinical circumstances. These agents are usually well tolerated. However, some subjects will experience allergic reactions to intravenous contrast. To lower the risk of allergic reactions, low allergenic contrast agents are administered at NIH clinical center. In addition, subjects will be advised that approximately 2-7% of patients who receive contrast agents will experience a temporary reduction in kidney function lasting up to 2 weeks following infusion and that in rare instances, permanent renal damage can result from the use of the IV contrasting agent. Therefore, in subjects with impaired kidney function, we will not use intravenous contrast.

#### **11.2.5. Risks related to pregnancy and nursing mothers**

There are no clinical studies in pregnant women, and it is unknown whether pembrolizumab is excreted in human milk. Men and women of child-bearing potential must use highly effective contraception as described in section 5.7.2. Pregnant or breastfeeding women are not eligible for this protocol. If a female subject or the partner of a male subject becomes pregnant, the sponsor must be notified. Male subjects should refrain from sperm donation.

#### **11.2.6. Risks related to central line placement**

When indicated, a catheter may be placed in a large vein of the neck, chest, or arm using local anesthetic. Patients will sign a separate consent for the placement procedure. Only trained experienced staff will place the line in order to minimize these procedure related risks.

The risks from the procedure are low; they include bleeding, bruising, or infection at the site of insertion. Some patient may experience a vasovagal reaction (lightheadedness, or, rarely, fainting due to temporary lowering of blood pressure). Very rarely (less than 1% of the time), the line placement may nick the lung causing it to

collapse during line insertion. If the lung collapses, a tube may have to be inserted into the chest and remain in place until the lung re-expands. Because of this risk, patients will have a chest x-ray following the procedure to make sure the line is in the correct place and that the lung is not collapsed. Once placed, the line will ideally remain in place until drug administration is complete.

#### **11.2.7. Risks related to bone marrow and skin punch biopsy**

The anesthetic can cause some temporary stinging and burning. A pulling sensation and discomfort may be felt as the sample is withdrawn. Although rare, there is a potential for bleeding at the site and local infection. Bleeding can be stopped by applying local pressure, and infection can be treated with antibiotics. In the long term minimal scarring may occur but in most cases the biopsy site is indistinguishable within a few months.

#### **11.2.8. Risks related to transfusions**

Some risks with the transfusion with blood and /or blood products include fever or allergic reactions. These risks are uncommon and are usually mild, but on rare occasions may be severe or life threatening. Extremely rare risks include infections with viruses, such as hepatitis or HIV or serious incompatibility reactions.

#### **11.2.9. Risks related to leukapheresis procedure**

The leukapheresis procedures will be performed in accordance with standard leukapheresis donation policies and procedures operative in the NIH department of transfusion medicine and will be in compliance with the Blood Donor Standards of the American Association of Blood Banks and the rules and regulations of the Food and Drug Administration. Adverse reactions to leukapheresis procedures are rare, but include:

- Pain and hematoma at the needle placement site.
- Vasovagal episodes, characterized by transient hypotension, dizziness, nausea and rarely, syncope are seen in less than 5% of the procedures. Hypotension secondary to volume depletion is known for the rare potential for a cerebrovascular or cardiovascular event.
- Cutaneous or circumoral parasthesias, chills, nausea, heartburn and rarely muscle spasms may result from the use of citrate anticoagulant used to prevent clotting in the extracorporeal circuit. Citrate reactions are usually relieved by slowing the rate of the anticoagulant infusion and by administering oral calcium carbonate tablets or with intravenous calcium solution.
- Subjects may receive hydroxyethyl starch (HES) to aid in the collection of cells. HES can rarely cause anaphylactoid reactions (hypersensitivity, mild influenza-like symptoms, bradycardia, tachycardia, bronchospasm, non-cardiogenic pulmonary edema), renal dysfunction, coagulopathy, and hypertension.

Prior to each leukapheresis, the potential risks associated with the procedure will be explained to the patient and a separate informed consent obtained.

#### **11.2.10. Risks related to genetic testing**

Accidental disclosure of genetic information derived from research testing will be unlikely as all samples and research data will be coded and kept separately from the patient demographic information. Individually identifiable genetic data directly related to this study will not be released to participants. If an unexpected but clinically relevant, inheritable DNA change (also known as an “incidental” or “secondary” finding) is discovered by research exome and/or genome sequencing we will consult with the IRB on the best way to handle this information and potentially share the need for confirmatory testing by a CLIA accredited facility with the patient. Patients may opt-out of receiving such notification of such secondary findings from research sequencing. With increasing technology, it is possible that a person may be identifiable from their sequence data submitted as part of a publication of this material. We will attempt to limit this, by again using only coded specimens.

### **11.3. Risks in Relation to Benefit**

Relapsed and refractory Acute Myeloid Leukemia is fatal without treatment. Even with the best available treatment it is fatal in the majority of cases. The benefits to the adult patient on this study could be a control, reduction or elimination of detectable AML potentially resulting in an improved quality of life, decreased transfusion requirements, a decreased susceptibility to infections, become eligible to receive additional therapy such as allogeneic transplant and foremost a significant improvement in survival time. Potentially, treatment with other therapies could also be avoided or postponed.

As of November 30, 2017 this study was closed to new subject accrual and in subject follow up only. As of March 15, 2019, the study will continue in data analysis only and the level of risk is minimal.

### **11.4. Informed consent processes and procedures**

The investigational nature and research objectives of this trial, the procedure and its attendant risks and discomforts will be carefully explained to the subject and a signed informed consent document will be obtained prior to entry onto this study.

At any time during participation in the protocol, should new information become available relating to risks, adverse events, or toxicities, this information will be provided orally or in writing to all enrolled or prospective patient participants. Documentation will be provided to the IRB and if necessary the informed consent amended to reflect relevant information.

### **11.5. Conflict of interest**

Merck is providing pembrolizumab and research funding for this study to NIH. No NIH investigator involved in this study receives any payment or other benefits from Merck. The principal investigator assures that each associate investigator listed on the protocol title page received a copy of the NIH's Guide to preventing conflict of interest. No members of the research team reported a potential conflict of interest. There are no conflicts of interest with any financial organization regarding the material mentioned in this protocol.

### **11.6. Technical Transfer Agreements**

The protocol will have the following tech transfer agreements: Cooperative Research and Development Agreement (CRADA) between NHLBI and Merck.

Material transfer agreement (MTA) with collaborators at Collaborative Health Initiative Research Program, Uniformed Services University School of Medicine who will conduct genomic sequencing on de-identified (coded) samples to determine molecular etiology of diseases encountered on this protocol.

Material transfer agreement (MTA) with collaborator at New York Genome Center who will conduct analysis of gene and protein expression on de-identified (coded) samples on this protocol.

## **12.0 PHARMACEUTICALS**

### **12.1. Pembrolizumab**

**Background Information:** Note for detailed and comprehensive background information please refer to the Investigator's Brochure.

**Investigational Product Name and Description:** Pembrolizumab is a humanized monoclonal antibody that blocks the interaction between PD-1 and its ligands, PD-L1 and PD-L2. Pembrolizumab is an IgG4 kappa immunoglobulin with an approximate molecular weight of 149 kDa.

**Preparation:** Pembrolizumab is provided as a white to off white lyophilized powder (50 mg/vial) or as a liquid solution (100 mg/vial) in Type I glass vials intended for single use only. Pembrolizumab Powder for Solution for Infusion, 50 mg/vial, is reconstituted with sterile water for injection prior to use.

The lyophilized drug product after reconstitution with sterile water for injection, and the liquid drug product are a clear to opalescent solutions, essentially free of visible particles. The reconstituted lyophilized product and the liquid product are intended for IV administration. The reconstituted drug product solution or the liquid drug product can be further diluted with normal saline or 5% dextrose in the concentration range of 1 to 10 mg/mL in intravenous (IV) containers made of polyvinyl chloride (PVC) or non-PVC material. Reconstituted vials should be immediately used to prepare the infusion solution in the IV bag and the infusion solution should be immediately administered. Diluted pembrolizumab solutions may be stored at room temperature for a cumulative time of up to 4 hours. This includes room temperature storage of admixture solutions in the IV bags and the duration of infusion. In addition, IV bags can be stored at 2 to 8°C for up to a cumulative time of 20 hours. This recommendation is based on up to 24 hours of room temperature and up to 24 hours of refrigerated stability data of diluted pembrolizumab solutions in the IV bags.

**Packaging, and Storage:** The drug product is stored as a stable lyophilized powder or liquid solution under refrigerated conditions (2 to 8°C).

**Administration:** The prescribed dose of pembrolizumab is given through an intravenous line containing a sterile, non-pyrogenic, low-protein binding 0.2 micron to 5 micron in-line or add-on filter. It is not allowed to co-administer other drugs through the same infusion line.

**Supply:** The drug product pembrolizumab is manufactured and supplied by Merck.

## 12.2. Decitabine

**Background Information:** Note for detailed and comprehensive background information please refer to the FDA product label.

**Product Name and Description:** Decitabine (5-aza-2'-deoxycytidine) is an analogue of the natural nucleoside 2'-deoxycytidine. Decitabine is a fine, white to almost white powder with the molecular formula of C8H12N4O4 and a molecular weight of 228.21. Its chemical name is 4-amino-1-(2-deoxy-β-D-erythro-pentofuranosyl)-1,3,5-triazin-2(1H)-one.

**Preparation:** Decitabine is a cytotoxic drug and caution should be exercised when handling and preparing. Procedures for proper handling and disposal of antineoplastic drugs should be applied. should be aseptically reconstituted with 10 mL of Sterile Water for Injection (USP); upon reconstitution, each mL contains approximately 5.0 mg of decitabine at pH 6.7-7.3. Immediately after reconstitution, the solution should be further diluted with 0.9% Sodium Chloride Injection or 5% Dextrose Injection to a final drug concentration of

0.1-1.0 mg/mL. Unless used within 15 minutes of reconstitution, the diluted solution must be prepared using cold (2°C - 8°C) infusion fluids and stored at 2°C - 8°C (36°F - 46°F) for up to a maximum of 4 hours until administration.

Parenteral drug products should be inspected visually for particulate matter and discoloration prior to administration, whenever solution and container permit. Do not use if there is evidence of particulate matter or discoloration.

**Packaging, and Storage:** Decitabine is supplied as a sterile, lyophilized white to almost white powder, in a single-dose vial, packaged in cartons of 1 vial. Each vial contains 50 mg of decitabine.

**Administration:** Decitabine is administered at a dose of 20 mg/m^2 by intravenous infusion over approximately 1 hour repeated daily for 10 days. This cycle should be repeated every 6 weeks. Patients may be premedicated with standard anti-emetic therapy. Store vials at 25°C (77°F); excursions permitted to 15-30°C (59-86°F).

**Supply:** Decitabine will be supplied by the NIH clinical center pharmacy. During the optional continuation phase decitabine may be supplied by another pharmacy.

### **12.3. Accountability procedures**

Drug accountability records will be maintained for all clinical supplies. All empty and partially used vials and clinical trial supplies will be destroyed locally according to the institution's standard operating procedures for drug destruction. The pharmacy will maintain detailed documentation of the number and identification of vials which are destroyed, and copies of these documents will be provided to the sponsor. Disposition of all unused boxes of study drug will be carried out according to instructions provided by the sponsor at the end of the study after drug accountability is performed by the study monitor.

## APPENDIX A: AML Diagnostic and Treatment Response Criteria

Acute Myeloid Leukemia (AML) is a clonal expansion of myeloid blasts in bone marrow, blood or other tissue, ICD-O code 9861/3.

### Diagnostic and Staging Criteria

**Bone marrow cellularity:** The volume of hematopoietic nucleated cells, expressed as a percentage of marrow volume less volume of fibrosis.

**Blasts:** For AML, the following cell types are considered equivalent to blasts and are included in the calculation of blast percentages. Note that erythroblasts are not counted as blasts in calculating blast percentages.

- Myeloblasts include both agranular and granular variants.
- Monoblasts and promonocytes for Acute Monoblastic and Monocytic Leukemia.  
Megakaryoblasts for Acute Megakaryoblastic Leukemia.

**Bone Marrow Blast Percentage:** calculated as the percent of blasts among all nucleated marrow cells.

**Residual Disease:** The NIH institutional standard for AML residual disease diagnosis is currently assessment with flow cytometry. Other clinically accepted methods of making this diagnosis exist (eg: Cytogenetics, FISH, RQ-PCR) and may be used at the discretion of the NIH attending pathologist.

### Response Definitions for AML:

1. **Measurable residual disease (MRD) negative complete remission.** No evidence of residual disease-after clinical assessment by flow cytometry (plus any other technique used in initial diagnosis of residual disease, if applicable). < 5% bone marrow blasts, no Auer rods, no evidence of extramedullary disease. This may be with (**mCR**) or without count recovery to ANC  $\geq$  1,000/mcl and platelet count  $\geq$  100,000/mcl (**mCRi**).
2. **Morphologic complete remission (CR):** ANC  $\geq$  1,000/mcl, platelet count  $\geq$  100,000/mcl, < 5% bone marrow blasts, no Auer rods, no evidence of extramedullary disease. (No requirements for marrow cellularity, hemoglobin concentration).
3. **Morphologic complete remission with incomplete blood count recovery (CRi):** Same as CR but ANC may be < 1,000/mcl and/or platelet count < 100,000/mcl.  
\*Patients with both an ANC < 1000/mcl and platelet count < 100,000/ mcl with at least a 10% marrow cellularity will be reported as a Morphological Leukemia Free State (MLFS).
4. **Partial remission (PR):** ANC  $\geq$  1,000/mcl, platelet count > 100,000/mcl, and at least a 50% decrease in the percentage of marrow aspirate blasts to 5-25%, or marrow blasts < 5% with persistent Auer rods.
5. **Stable disease (SD):** The absence of a complete or partial response, and no progressive disease.
6. **Progressive disease (PD):** Defined as ONE of the following:
  - Greater than 50% relative increase in blasts in the peripheral blood or bone marrow from best assessment with minimum threshold of 20% blasts in the marrow or  $1.0 \times 10^9/L$  blasts in peripheral blood.
  - Development of biopsy proven extramedullary leukemia (if the subject has extramedullary disease at baseline, then PD will be defined by blood and marrow criteria or if new sites of extramedullary disease appear).
  - If subject who present with an initial marrow blast percentage sufficiently high to preclude the ability to base disease progression on a >50% increase in marrow blast percentage, disease progression should be based on peripheral blood criteria or development of extramedullary leukemia as above.
7. **Not Evaluable:** Data incomplete or inadequate for time-point or overall assessment.

Note: Patients entering this study already in morphologic complete remission (ie: CR or CRi) but with evidence of residual disease the only responses possible are mCR, mCRi, SD, PD or NE (see above).

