### 5.8.2. Off-Study Criteria

A subject must be removed *from the study* for any of the following reasons:

- Confirmed disease progression despite at least two cycles of hypomethylating agent therapy and/or four doses of pembrolizumab. For these purposes disease progression is defined as greater than 50% relative increase in blasts in the peripheral blood or bone marrow or development of extramedullary disease (see Appendix A) at a therapy response assessment time-point (see Appendix G) compared to before start of treatment or relapse in those previously in complete remission (mCR/mCRi, CR/CRi).
- Patient meets off-treatment criteria but is not eligible, or declines, active surveillance phase
- The subject has a confirmed positive serum pregnancy test
- Subject becomes significantly noncompliant with study drug administration, study procedures, or study requirements, which might increase risk or substantially compromise the interpretation of study results.
- The subject is lost to follow-up
- The subject completes two years on study
- Administrative reasons
- The subject or legal representative (such as a parent or legal guardian) withdraws consent
- Investigator's decision to withdraw the subject from the study

The end of treatment and follow-up visit procedures are listed in Section 6.

The End of Treatment and Follow-up visit procedures are listed in Section 6. After the end of treatment, each subject will be followed for 30 days for adverse event monitoring. Subjects who discontinue for reasons other than progressive disease will have post-treatment follow-up for disease status until disease progression, initiating another cancer treatment, withdrawing consent or becoming lost to follow-up. After study withdrawal each subject will be offered the opportunity to consent to an alternative hematology branch protocol (eg: 94-H-0010) to allow follow-up by telephone at approximately three monthly intervals for overall survival until death, withdrawal of consent, or the closing of the study protocol, whichever occurs first.

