## APPENDIX G: Scheduled Clinical Assessments

Trial Period:	Screening Phase	Induction Phase Treatment (Assessment at end of cycle...)								Post-Induction	
		1	2	3	4	5	6	7	8	SFV / Off-study Visits	Contin. Phase (q3mo)
Pre-screening and Consents	X										
Inclusion/Exclusion Criteria	X										
Demographics and Full Medical History	X										
Interval Medical History		X	X	X	X	X	X	X	X	X	X
Focused Physical Exam		X	X	X	X	X	X	X	X	X	X
ECOG Performance Status	Baseline	X	X	X	X	X	X	X	X	X	X
Structured Review of Adverse Events	Baseline	X	X	X	X	X	X	X	X	X	X
Prior and Concomitant Medication Review	X	X	X	X	X	X	X	X	X	X	X
Trial Treatment Administration Log		X	X	X	X	X	X	X	X		
Therapy Response Assessment	X		X		X		X		X	X	X
Bone Marrow Examination* (flow cytometry, morphology)	X		X		X		X		X		
Cytogenetics (bone marrow)	X		If+ @BL		If+ @BL		If+ @BL		X		
Pregnancy Test -- Urine or Serum $\beta$ -HCG	W/in 72 hours of first dose.	X	X	X	X	X	X	X	X	X	X
Acute Care, Mineral and Hepatic Panels	W/in 14 days of first dose	X	X	X	X	X	X	X	X	X	X
Total protein, CK, Uric Acid, LDH, PT, PTT, Fibrinogen, CBC w/ diff, Reticulocyte, Type&Screen.	X	X	X	X	X	X	X	X	X	X	X
CMV IgG, IgM and PCR, HIV serology, Hepatitis serologies,	X										
Thyroid Function (T3, FT4 and TSH), EKG, HLA typing, Urinalysis	X										
Peripheral Blood Flow Cytometry (T/B/NK and AML)	X		X		X		X		X		

"If + @ BL" = Cytogenetics will be checked after cycles 2, 4 and 6 only if abnormal at baseline.

\* = an additional bone marrow examination assessment will be performed on cycle 1 day 8 (+/- 3 days).

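### Appendix A defines CR, CRi and PR without looking at blood blasts or excluding progression, so a patient with circulating blasts can score CR or CRi, and one assessment can be PR (or CR) and PD at once

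*Combined protocol and SAP*

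**What the plan says.** Table 7 in Section 6.3 takes the efficacy endpoint from Appendix A and counts mCR, mCRi, CR, CRi and PR as responses. Time to first and best response, and both durations, are built on those categories.

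Appendix A, Response Definitions for AML, gives these conditions:

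- **CR:** ANC at least 1,000/mcl and platelets at least 100,000/mcl, with "< 5% bone marrow blasts, no Auer rods, no evidence of extramedullary disease. (No requirements for marrow cellularity, hemoglobin concentration").
- **CRi:** "Same as CR but ANC may be < 1,000/mcl and/or platelet count < 100,000/mcl".
- **mCR/mCRi:** "No evidence of residual disease-after clinical assessment by flow cytometry", plus the marrow, Auer rod and extramedullary conditions. The specimen for flow cytometry is not named.
- **PR:** ANC at least 1,000/mcl, platelets above 100,000/mcl, and "at least a 50% decrease in the percentage of marrow aspirate blasts to 5-25%, or marrow blasts < 5% with persistent Auer rods". The reference for the decrease is not stated.
- **PD:** "Greater than 50% relative increase in blasts in the peripheral blood or bone marrow from best assessment", with a floor of 20% in marrow or 1.0 x10^9/L in blood, or extramedullary leukemia.
- **SD:** neither a response nor progression. It is the only category written to exclude PD.

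No order of precedence is given. Section 5.8.2 has its own progression test for leaving the study, which also counts "greater than 50% relative increase in blasts in the peripheral blood or bone marrow" but compares with the value before treatment. Appendix G schedules "Peripheral Blood Flow Cytometry (T/B/NK and AML") at screening and after cycles 2, 4, 6 and 8, without linking it to CR, CRi or PR.

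**The concern.** The plan treats blood as a site of disease when it calls progression, but does not look there when it calls CR, CRi or PR. This has two consequences. A patient with leukemic blasts still circulating can be reported in complete remission. And because CR, CRi and PR do not exclude PD, two people applying Appendix A correctly to the same data can report different categories.

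The outputs at stake are the response proportion, time to response and duration of response. For duration, an assessment that is both PR and PD either continues the response or ends it, and the plan does not say which. All of these are secondary and descriptive, so no error rate or power is affected.

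**Working it through.** There is no figure in the plan to reproduce. The check applies the Appendix A definitions to hypothetical patients, none of them taken from the documents.

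**Rules applied**

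- CR: marrow < 5%, no Auer rods, no extramedullary disease, ANC >= 1,000/mcl and platelets >= 100,000/mcl. CRi: the same without full count recovery.
- PR: ANC >= 1,000/mcl, platelets > 100,000/mcl, marrow 5-25% and (now / baseline) <= 0.5. Baseline as the reference is my assumption. The Auer rod route to PR is not needed here.
- PD: (now / best) > 1.5 and either marrow >= 20% or blood >= 1.0 x10^9/L, each judged in its own compartment.

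All patients have ANC 1,500/mcl, no Auer rods, no extramedullary disease and, except patient 5, residual disease on flow cytometry. Platelets are 120,000/mcl except in patient 2. For patients 1 to 4 the best earlier value is the baseline value.

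| Patient | Response rule | PD rule | As written | Under the fix |
|---|---|---|---|---|
| 1. Marrow 40% to 3%; blood 0.4 to 0.5 | CR met | 0.5/0.4 = 1.25: not met | CR | SD |
| 2. As 1, platelets 60,000 | CRi met | not met | CRi | SD |
| 3. Marrow 40% to 3%; blood 0.6 to 1.2 | CR met | 1.2/0.6 = 2.0 and 1.2 >= 1.0: met | CR and PD | PD |
| 4. Marrow 40% to 15%; blood 0.5 to 1.2 | 15/40 = 0.375: PR met | 1.2/0.5 = 2.4 and 1.2 >= 1.0: met | PR and PD | PD |
| 5. Marrow 60% baseline, 10% best, 24% now; no blood blasts | 24/60 = 0.40: PR met | 24/10 = 2.4 and 24 >= 20: met | PR and PD | PD |

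The count conditions matter. Patient 4 with platelets of 60,000/mcl would not meet PR and would be PD only.

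Patient 5 shows that a blood-blast clause alone does not separate the categories. PR allows marrow blasts up to 25% while PD starts at 20%, and here the two use different reference points. A condition excluding PD is needed as well.

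**Against Section 5.8.2.** If 0.5 is the value before treatment, patient 4's rise of (1.2 - 0.5)/0.5 = 140% also meets that section's blast increase. Patient 5 does not: 24% is below the pre-treatment 60%. So patient 5 is PD under Appendix A but has no blast progression under Section 5.8.2.

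**Size.** With n = 10, one patient is 1/10 = 10 percentage points. The exact (Clopper-Pearson) 95% limits are the 0.025 quantile of Beta(x, n - x + 1) and the 0.975 quantile of Beta(x + 1, n - x):

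- x = 3: 30%, 6.7% to 65.2%
- x = 2: 20%, 2.5% to 55.6%

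**The case against.** **Every remission category is affected.** A reader might infer this, since mCR/mCRi has no explicit blood clause either. The documents do not support it in practice: those categories need no residual disease on flow cytometry, and a patient with circulating AML blasts would hardly satisfy that. What stands is that the specimen is not named. Patients who enter already in CR or CRi with residual disease are also outside the gap, because Appendix A does not allow them CR, CRi or PR as a response.

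**Continuation of treatment rests on a wrong category.** This is also too strong. Section 5.9 offers continuation to SD as well as to the responses, so patients 1 and 2 qualify either way. Only an overlap with PD could matter, and Section 5.8.2 separately removes patients with confirmed progression after a stated minimum of treatment. That answers the point only in part, because its reference differs from Appendix A's.

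**Marrow and blood are a week apart.** Section 6.3 lets the marrow be taken in the week before the next pembrolizumab dose, and Section 6.2 gives the blood tests a window of 3 days either way. A gap is possible, not planned. Marrow cellularity after decitabine has no bearing on blood blasts.

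**Nothing in the documents says that remission must exclude blood blasts.** True, and to that extent the CR/CRi condition is a judgement. But Appendix A's own description of AML lists blood as a disease site separate from other tissue, and PD lists blood blasts separately from extramedullary leukemia, so the extramedullary clause does not clearly cover them. Table 7's reference to conventional criteria points back to Appendix A and imports nothing further. The overlap with PD needs no outside standard.

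**It is a small descriptive endpoint, and any reclassification among 10 patients moves 10 points.** Correct. That limits the weight of the point but does not remove the contradiction.

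**Conclusion.** The concern holds for CR, CRi and PR. As written, circulating blasts do not prevent CR or CRi, and with the required count recovery one assessment can be PR and PD, or CR and PD. PR and PD can also coincide on marrow alone. Nothing in Sections 5.8.2 or 6.3 or Appendix G resolves this. These are stated rules that give conflicting categories, which is more than missing detail.

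The effect is confined to response, time to response and duration of response. One affected patient moves the proportion by 10 points, hypothetically from 3/10 to 2/10, and the intervals overlap heavily. The documents give no frequency, so the number affected may be zero. The PR examples assume that the decrease is measured from baseline.

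**What to change.** For response tabulation only (response, time to response, duration of response):

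1. Score CR or CRi only if the blood differential at the same assessment shows no leukemic blasts, and state which differential is paired with each marrow.
2. Score CR, CRi or PR only if no Appendix A PD criterion is met at that assessment. Where both are met, tabulate PD.
3. State the reference for the PR decrease, and name the flow cytometry specimen for mCR/mCRi.

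Section 11.3 says that accrual closed on November 30, 2017 and that from March 15, 2019 only data analysis remains. The change is therefore post hoc. Present it as a labelled analysis convention, and list each patient whose category differs from Appendix A as written, with both categories shown.

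No new test is needed: the blood differential is scheduled with every cycle, and blood flow cytometry after cycles 2, 4, 6 and 8. The cost is a short re-adjudication and possibly a slightly lower response count. A patient with a cleared marrow but residual blood blasts (patient 1 above) becomes SD, which some readers will find severe; the listing makes that visible.

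Separately, the sponsor should reconcile Section 5.8.2, Section 5.9 and Appendix A. Progression is measured from before treatment in Section 5.8.2 and from best assessment in Appendix A, whose categories Section 5.9 uses for continuation. The convention above is not a rule for treatment, and none is proposed.
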